5.10 Treatment Beyond Progression

A minority of participants treated with immunotherapy may derive clinical benefit as either delayed responses, stable disease, or increased overall survival despite initial evidence of progressive disease (PD) with pembrolizumab and eribulin.

Participants may be permitted to continue treatment beyond initial RECIST 1.1-defined PD that occurs during the initial (24 weeks) of treatment as long as they meet the following criteria:

- No more than 4 new lesions, total sum of the longest diameter (SHORT diameter for LN) cannot exceed 40% of the initial sum including new lesions
- Participants must be clinically stable with no change in performance status due to disease progression
- No indication for immediate alternative treatment, however, palliative radiation to isolated symptomatic lesions is allowed
- Participant [assessed by the investigator] is showing clinical benefit and tolerates study drug. The assessment of clinical benefit should take into account whether the participant is clinically stable or deteriorating and likely or unlikely to receive ^[1]_{SEP} further benefit from continued treatment.
- The time of progression is noted from the first assessment that exceeds standard criteria

New lesions are considered measurable at the time of initial progression if the longest diameter is at least 10 mm (except for pathological lymph nodes, which must have a short axis of at least 15 mm). Any new lesion considered non-measurable at the time of initial progression may become measurable and therefore be included in the tumor burden measurement if the longest diameter increases to at least 10 mm (except for pathological lymph nodes, which must have an increase in short axis to at least 15 mm).

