5.5 Duration of Therapy

Duration of therapy will depend on individual response, evidence of disease progression and tolerance. In the absence of treatment delays due to adverse event(s), treatment may continue for 2 years or 35 cycles of therapy or until one of the following criteria applies:

- Disease progression in any participant who showed first radiologic evidence of progressive disease (PD) by RECIST 1.1 (see Section 11.1.4) and is deemed clinically stable, it is at the discretion of the investigator to continue treating the participant until progression is confirmed at least 4 weeks from the date of the first radiologic evidence of PD. Further details are described below.
- Intercurrent illness that prevents further administration of treatment
- Unacceptable adverse event(s) which include the following (see also section):
 - Any Grade 2 drug-related uveitis or eye pain or blurred vision that does not respond to topical therapy and does not improve to Grade 1 severity within the re-treatment period OR requires systemic treatment
 - Participants requiring > two dose delays for the same type of event should be removed from protocol
 - Any adverse event, laboratory abnormality, or intercurrent illness which, in the judgment of the investigator, presents a substantial clinical risk to the participant with continued study drug dosing
 - Any dosing interruption lasting >5 weeks, with the following exceptions:
 - Participants being tapered after high dose corticosteroids over one month followed by a two-week observation period will be allowed an additional two weeks to restart treatment (a maximum eight-week interruption).
 - Dosing interruptions >5 weeks that occur for non-drug-related reasons may be allowed if approved by the Investigator. Prior to re-initiating treatment in a participant with a dosing interruption lasting >5 weeks, the PI must be consulted.
 - Grade 2 pneumonitis requiring steroids.
 - Grade 3 or Grade 4 drug-related autoimmune or inflammatory events including uveitis, pneumonitis, diarrhea, colitis, neurologic adverse events, hypersensitivity reaction, or infusion reaction of any duration requires discontinuation except as noted below:
 - Any other grade 3 non-skin, drug-related AE lasting >7 days including fatigue.

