For any participant who shows first radiologic evidence of progressive disease (PD) by RECIST1.1 (see Section 11.1.4) and is deemed clinically stable, it is at the discretion of the investigator to continue treating the participant until progression is confirmed at least 4 weeks from the date of the first radiologic evidence of PD. If progression is confirmed, the participant will be discontinued from study treatment. If progression is not confirmed on the subsequent scan, the participant should continue to receive study treatment and have radiographic scans performed every 6 weeks if the participant has been on study for less than 24 weeks, or every 9 weeks for participants who have been on study greater than 24 weeks to monitor disease status. Any participant who had initial radiologic progression and is deemed clinically unstable should be discontinued from both study drugs and no subsequent scan for confirmation is required. Exceptions may be considered to continue treatment in the presence of clinically stable or improved condition only after consultation with the PI.

For purposes of PFS assessment on this trial, in addition to radiographic assessment of tumor response or progression, the investigator should take into account the clinical condition/stability of participants. Clinically stable is defined by the following criteria:

- Absence of signs and symptoms (including worsening of laboratory values) indicating disease progression

- No decline in ECOG performance status
- Absence of rapid progression of disease
- Absence of progressive tumor(s) at critical anatomical sites (eg, cord compression) requiring urgent alternative medical intervention

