For any participant who showed first radiologic evidence of progressive disease (PD) by RECIST 1.1 and is deemed clinically stable, it is at the discretion of the investigator to continue treating the participant until progression is confirmed at the next scheduled restaging (or with a confirmatory completed at least 4 weeks from the initial date of PD). If progression is not confirmed on the subsequent scan, the participant should continue to receive treatment and have radiographic scans performed according to the study calendar (every 6 weeks). If radiologic progression is confirmed, then the participant should be discontinued from all study treatment. If the treating investigator feels that the participant is clinically stable, demonstrates improved condition, or is clearly continuing to benefit from the treatment; the PI may approve the participant to continue to receive study treatment. In all participants, the date of progression will be documented as the first date progression was observed.

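### The 40% tumor-burden limit in Section 5.10, taken at its words, bars nearly everyone the section is meant to admit, and no other text settles what was intended

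*Combined protocol and SAP*

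**What the plan says.** Section 5.10 permits continued treatment "beyond initial RECIST 1.1-defined PD that occurs during the initial (24 weeks) of treatment" when several conditions hold. One condition joins a ceiling of four new lesions to a size limit: "total sum of the longest diameter (SHORT diameter for LN) cannot exceed 40% of the initial sum including new lesions". The others are clinical stability with unchanged performance status, no need for immediate alternative treatment, and benefit and tolerance as judged by the investigator. The section treats a new lesion as measurable from 10 mm (15 mm short axis for nodes). A lesion that starts out too small "may become measurable and therefore be included in the tumor burden measurement" once it reaches that size.

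Two other places govern the same decision. The first stopping criterion in Section 5.5 concerns "Disease progression in any participant who showed first radiologic evidence of progressive disease (PD) by RECIST 1.1". For clinically stable participants, 5.5 says that "it is at the discretion of the investigator to continue treating the participant until progression is confirmed at least 4 weeks" after the first scan showing it. Section 11.1 says that "it is at the discretion of the investigator to continue treating the participant until progression is confirmed at the next scheduled restaging", or on a scan at least 4 weeks later. Neither section cites 5.10.

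Sections 5.10 and 11.1 both date progression at the first assessment that shows it, whether or not treatment continues.

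**The concern.** A rule for treating beyond progression has to admit at least some people who have just progressed. Progression under RECIST 1.1 normally means that tumor burden has grown or that new lesions have appeared. A ceiling of 40% of the starting sum asks for the opposite: a burden well below where the participant began.

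An investigator applying the printed words would stop nearly everyone. One who assumes a drafting slip must guess which rule was meant. Two investigators could then decide differently on identical scans, and nobody could say afterwards which decision was a protocol deviation. What is at stake is exposure to eribulin and pembrolizumab after progression, and consistency across participants.

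**Working it through.** The plan gives no worked figure for this clause, so there is none to reproduce. The check sets the cap against the plan's own definition of progression.

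**Inputs.** From 5.10: cap of 40% of the initial sum, new lesions counted; smallest measurable new lesion 10 mm. From 11.1.4.1: target progression is a rise of at least 20% and at least 5 mm over the smallest sum on study; any new lesion is also progression. Write B for the baseline sum and N for the smallest sum on study.

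**Step 1: the printed words, target-lesion progression.** The smallest possible sum at progression is max(1.2N, N + 5 mm). The cap is 0.40B. Where the 20% rule governs, 1.2N ≤ 0.40B gives N ≤ 0.40/1.2 = 0.333B, which is prior shrinkage of at least 66.7%. For B = 100 mm the cap is 40 mm:

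| Smallest sum N | Minimum sum at progression | Within 40 mm? |
|---|---|---|
| 100 mm (no shrinkage) | 120 mm | no |
| 70 mm (a 30% response) | 84 mm | no |
| 50 mm | 60 mm | no |
| 34 mm | 40.8 mm | no |
| 33 mm | 39.6 mm | yes |

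For small baselines the 5 mm rule governs and the requirement is stricter. With B = 50 mm the cap is 20 mm, so N + 5 ≤ 20 gives N ≤ 15 mm, a 70% shrinkage.

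**Step 2: the printed words, progression by new lesion.** With B = 100 mm, unchanged targets and one 10 mm new lesion, the total is 110 mm against 40 mm. It passes only if the targets are at 30 mm or less. If progression adds nothing to the sum (a non-measurable new lesion, or non-target progression), the targets must still be at 40 mm or less. By every route the total has to be at least 60% below baseline.

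**Step 3: the workable readings.** Take B = 100 mm.

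- A: the total including new lesions may rise by at most 40%, so total ≤ 140 mm.
- B: new lesions may total at most 40% of the initial sum, so new ≤ 40 mm.
- C: the limit refers to the sum at first progression. It then restrains later growth and tests nothing at first progression itself. Assuming it means a 40% increase, the later ceiling is 1.4 times that sum.

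| At first progression | A | B | C |
|---|---|---|---|
| target 120 + new 35 = 155 mm | barred | allowed | not tested; later ceiling 1.4 × 155 = 217 mm |
| target 90 + new 45 = 135 mm | allowed | barred | not tested; later ceiling 1.4 × 135 = 189 mm |

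Both cases fit within four new lesions. Under A, target growth of 20% to 40% from an unshrunken baseline (120 to 140 mm) would pass, so the criterion would separate limited from large growth.

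**Step 4: does the text choose?** For A: 5.10 goes on to count new measurable lesions in tumor burden, and 11.2.1.4 (irRECIST) compares target plus new measurable lesions with baseline. For B: the size limit directly follows the new-lesion count, so it can be read as describing those lesions. For C: 5.10 uses the word initial for first progression, and a baseline sum contains no new lesions. A seems likeliest, but nothing in the documents defines the 40% rule.

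**Step 5: 5.10 beside 5.5 and 11.1.** Clinical stability, performance status and absence of an urgent need for other treatment have counterparts in 5.5. Three limits appear only in 5.10: first progression within 24 weeks, at most four new lesions, and the burden cap. The nearest 5.5 comes to a burden limit is the unquantified "Absence of rapid progression of disease".

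**The case against.** The strongest reply is that the clause is ambiguous rather than broken. Reading B is available on the printed words and can be met, and even the strict reading is not impossible, since a deep responder could satisfy it. This stands in part. A reader might infer that the criterion can never be met; Step 1 shows otherwise. But the strict reading still defeats the section's purpose, which is to serve people with initial progression who may respond late or remain stable. Ambiguity among the alternatives is itself a reason to rewrite.

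Second, 5.10 is the section devoted to treatment beyond progression, so its conditions ordinarily narrow the general discretion in 5.5 and 11.1. This stands. Nothing in 5.5 or 11.1 says that the 5.10 limits do not apply. A reader might infer a contradiction, particularly because 5.5 schedules scans "every 9 weeks for participants who have been on study greater than 24 weeks to monitor disease status". That does not follow. A participant with first progression at week 22 has a confirmatory scan at week 26 or later (22 + 4), and if progression is not confirmed needs exactly that interval. It is compatible with the 24-week window. What remains is a missing cross-reference.

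Third, the strict reading errs toward stopping treatment, and continuation is bounded in any case by clinical stability, the confirmatory scan, and consultation with or approval by the principal investigator. This is correct and limits the seriousness of the point.

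**Conclusion.** The point holds for the wording of the 40% clause. As printed, it admits target-lesion progression only after shrinkage to one third of baseline or less, and requires a total at least 60% below baseline by any route. This follows from the protocol's own definitions; the millimeter examples assume a 100 mm baseline unless stated. At least three workable readings exist, and the worked cases show that they disagree. Preferring a 40% rise over baseline is a judgement about plausibility; the documents do not establish it.

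The link to 5.5 and 11.1 is secondary. An investigator working from either section would not learn of three limits that apply.

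A reader might infer that the primary result is at risk. It is not. Progression is dated at first observation, and 13.1 counts progression within 12 weeks as failure regardless of later treatment. The 12-week progression-free rate, the rule of 9 of 19 and PFS are the same under every reading. The documents do not allow an estimate of how many participants would be handled differently. The clause should be corrected, but it does not threaten the trial's efficacy conclusions.

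**What to change.** Replace the clause with an explicit rule, most plausibly: *the total sum of diameters, including new measurable lesions, may not increase by more than 40% over the baseline sum*. The sponsor should confirm two things: that an increase is meant, and whether the reference is the baseline sum or the sum at first progression.

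Add one sentence to 5.5 and one to 11.1 stating that continuation after first RECIST 1.1 progression is subject to 5.10, including its 24-week window and four-lesion limit.

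The cost is one reworded criterion and two cross-references; sample size, analysis and data collection are untouched. The protocol notes that long-term follow-up is being terminated and does not say whether anyone is still on treatment. If nobody is, a short clarification recording which reading was applied would let post-progression treatment and deviations be reported consistently.

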5.11 Lifestyle Restrictions

5.11.1 Meals and Dietary Restrictions

Participants should maintain a normal diet unless modifications are required to manage an AE such as diarrhea, nausea or vomiting.

5.11.2 Contraception

Pembrolizumab or Eribulin may have adverse effects on a fetus in utero. Refer to Appendix G for approved methods of contraception.

For this study, male participants will be considered to be of non-reproductive potential if they have azoospermia (whether due to having had a vasectomy or due to an underlying medical condition).

5.11.3 Pregnancy

If a participant inadvertently becomes pregnant while on treatment with pembrolizumab or Eribulin, the participant will be immediately discontinued from study treatment. The site will contact the participant at least monthly and document the participant's status until the pregnancy has been completed or terminated. The outcome of the pregnancy will be reported to Merck within 2 working days if the outcome is a serious adverse experience (eg, death, abortion, congenital anomaly, or other disabling or life-threatening complication to the mother or newborn). The study Investigator will make every effort to obtain permission to follow the outcome of the pregnancy and report the condition of the fetus or newborn to Merck and Eisai. If a male participant impregnates his female partner, the study personnel at the site must be informed immediately and the pregnancy must be reported to Merck and followed as described in Section 7.6.

5.11.4 Use in Nursing Women

It is unknown whether pembrolizumab is excreted in human milk. Eribulin may be excreted in human milk. Since many drugs are excreted in human milk, and because of the potential for serious adverse reactions in the nursing infant, participants who are breast-feeding are not eligible for enrollment.

6. DOSING DELAYS/DOSE MODIFICATIONS

Dose delays and modifications will be made as indicated in the following table(s). The descriptions and grading scales found in the revised NCI Common Terminology Criteria for Adverse Events (CTCAE) version 5.0 will be utilized for dose delays and dose modifications. A copy of the CTCAE version 5.0 can be downloaded from the CTEP website http://ctep.cancer.gov/protocolDevelopment/electronic_applications/ctc.htm.

Dosing interruptions are permitted in the case of medical / surgical events or logistical reasons not related to study therapy (e.g., elective surgery, unrelated medical events, participant vacation, and/or holidays). Participants should be placed back on study therapy within 5 weeks of the scheduled interruption, unless otherwise discussed with the Sponsor. The reason for interruption should be documented in the participant's study record.

Dose modifications and delays for eribulin will be allowed and are described below. No re-escalation will be allowed for eribulin. Dose delays for pembrolizumab for adverse events are described below. There are no dose reductions of pembrolizumab allowed. See Section 5.9 for guidelines regarding resumption of pembrolizumab following dose delays.

For toxicities in this Section which are attributable to pembrolizumab alone, only pembrolizumab should be held as directed. It is permissible to continue eribulin despite discontinuation of pembrolizumab in these select cases. This will be left to the treating physician's discretion after discussion and approval of the study PI.

For toxicities in this Section which are attributable to eribulin alone, only eribulin should be held

as directed. It is permissible to continue pembrolizumab despite discontinuation of eribulin in these select cases. This will be left to the treating physician's discretion after discussion and approval by the study PI.

6.1 Eribulin dosing delays/dose modifications

Participants should be carefully monitored for toxicity. If a treatment delay is required for eribulin toxicity or if treatment with eribulin is withheld permanently, treatment with pembrolizumab is allowed. Dosing levels for eribulin are shown in Table 2. Eribulin toxicities should be managed according to the guidelines in Tables 3.1 through 3.5. Once reduced, the dose of eribulin will not be re-escalated.

Clinical judgement should be used to determine appropriate management of the patient during any adverse event. Temporary interruption, dose reduction or permanent discontinuation of Eribulin should be considered if clinically indicated.

Table 2. Eribulin dosing levels

Dose Level	Eribulin Dose
Starting dose	$1.4\text{mg}/\text{m}^2$ (1 cycle = 21 days)
1 st dose reduction	$1.1\text{ mg}/\text{m}^2$
2 nd dose reduction	$0.7\text{ mg}/\text{m}^2$

- Toxicities graded in accordance with National Cancer Institute Common Toxicity Criteria for AEs, version 5.0
- Discontinuation of eribulin is required if a dose reduction to less than $0.7\text{ mg}/\text{m}^2$ is required.
- A minimum of 6 days between Day 1 and Day 8 of eribulin administration will be required. Day 8 administration of Eribulin must not be given prior to Day 8. A minimum of 13 days between Day 8 and Day 1 of next cycle will be required.
- If a participant does not meet criteria to receive Day 8 of eribulin, the Day 8 dose should be skipped (i.e., it will not be made up on Day 15) for that cycle.
- Once a dose is reduced, it should not be re-escalated.
- Treatment with eribulin will be discontinued if participants require a delay greater than 5 weeks.
- QTc prolongation has been observed in patients receiving eribulin. Cardiac monitoring, including EKG, will be performed per institutional standard of care.

Table 3.1 Eribulin Diarrhea Toxicity Dose Modification

Diarrhea	Management/Next Dose for Eribulin
≤ Grade 2	No dose modification

Diarrhea	Management/Next Dose for Eribulin
Grade 3, first occurrence	Hold eribulin until recovery to grade < 2. Maximize supportive care measures. If symptom recovery occurs within 1 week, then eribulin may be resumed at the same dose if deemed appropriate by the investigator, otherwise, reduce by 1 dose level.
Grade 3, despite maximal supportive measures	Hold eribulin until recovery to grade < 2 then reduce by 1 dose level.
Grade 4	Hold eribulin until recovery to grade < 2 then reduce by 1 dose level.

Table 3.2 Eribulin Peripheral Neuropathy Dose Modification

Peripheral Neuropathy	Management/Next Dose for Eribulin
≤ Grade 1	No dose modification
Grade 2	For intolerable (as determined by physician and participant) grade 2, decrease eribulin by one dose level.
Grade 3	Hold eribulin until recovery to grade < 2 then reduce by 1 dose level.
Grade 4	Permanently discontinue eribulin.

Table 3.3 Eribulin Neutropenia Dose Modification

Neutropenia	Management/Next Dose for Eribulin
ANC < 500 cells/mm ³ lasting > 7 days with or without use of growth factors	Hold eribulin until recovery to grade < 2 and reduce by 1 dose level. Prophylactic growth factor support should be instituted for subsequent cycles.
ANC < 500 cells/mm ³ lasting ≤ 7 days without use of growth factors	Hold eribulin until recovery to grade < 2. Resume eribulin at the same dose. Growth factor support should be provided.
ANC < 500 cells/mm ³ lasting ≤ 7 days in despite use of growth factors	Hold eribulin until recovery to grade < 2, and reduce by 1 dose level. Continue ongoing prophylactic growth factor support for subsequent cycles.
ANC < 1000 /mm ³ with fever or infection without use of growth factors	Hold eribulin until recovery to grade < 2. Resume eribulin at the same dose. Growth factor support should be provided.
ANC < 1000 /mm ³ with fever or infection despite use of growth factors	Hold eribulin until recovery to grade < 2, and reduce by 1 dose level. Growth factor support should be provided.
ANC < 1000 /mm ³ without fever or infection	First occurrence: Hold eribulin until recovery to grade < 2 then resume at the same dose. Growth factor support should be provided. If uncomplicated neutropenia (<1000 /mm ³ without fever or infection) occurs/recurs despite growth factor support, then hold eribulin until recovery to grade < 2. Eribulin may be then be resumed at the same dose with growth factor support, or it may be reduced by one dose level. If a participant misses two consecutive Day 8 eribulin doses due to uncomplicated neutropenia, then hold eribulin until

Neutropenia	Management/Next Dose for Eribulin
	recovery to grade < 2, reduce by 1 dose level, and consider prophylactic growth factor support for subsequent cycles.
ANC = absolute neutrophil count	

Table 3.4 Eribulin Thrombocytopenia Dose Modification

Thrombocytopenia	Management/Next Dose for Eribulin
≤ Grade 1	No dose modification
Grade 2	Hold eribulin until recovery to grade < 2.
Grade 3	Hold eribulin until recovery to grade < 2 then reduce by 1 dose level.
Grade 4	Hold eribulin until recovery to grade < 2 then reduce by 1 dose level.

Table 3.5 Eribulin Anemia Dose Modification

Anemia	Management/Next Dose for Eribulin
≤ Grade 1	No dose modification
Grade 2	No dose modification
Grade 3	No dose modification
Grade 4	Hold eribulin until recovery to grade < 2 then reduce by 1 dose level. PRBC transfusions are permitted to treat anemia on protocol.

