5.3.2 Pembrolizumab

Pembrolizumab will be administered by trained medical personnel at the investigational site. Treatment compliance will be monitored through documentation of study treatment administration in the participant's medical record.

Pembrolizumab will be administered in the outpatient clinic on Day 1 of each cycle. Pembrolizumab should be prepared and administered as an approximately 30-minute IV infusion per institutional standard, infuse prior to Eribulin

Please refer to the FDA-approved package insert for pembrolizumab for product information and a comprehensive list of adverse events. Pembrolizumab should be prepared and administered per institutional standard. Institutional standard procedures include BSA calculations, body weight assessments and dose calculations/recalculations. Infusion times may be prolonged in participants who experience an infusion reaction as per section 5.9.

Pembrolizumab should be administered prior to eribulin administration. There should be no overlap in timing of the two administrations.

The standard dose of pembrolizumab is 200mg IV.

5.3.3 *Discontinuation of eribulin*

If eribulin is stopped for toxicity, participants are permitted to continue protocol therapy with pembrolizumab alone.

5.3.4 *Discontinuation of pembrolizumab*

If pembrolizumab is stopped for toxicity, participants are permitted to continue protocol therapy with eribulin alone.

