 - Any grade 3 or 4 drug-related laboratory abnormality or electrolyte abnormality, not associated with underlying organ pathology, that does not require treatment except for electrolyte replacements **does not** require treatment discontinuation.
 - Grade 3 amylase or lipase abnormalities that are not associated with diabetes mellitus (DM), associated liver or gall bladder inflammation clinical manifestations of pancreatitis and which decrease to < Grade 2

within 1 week of onset **may** resume study treatment when resolved.

- Any grade 4 events except as noted above.
- Any participants who require additional immune suppressive treatment beyond steroids should go off study treatment
- Participant demonstrates an inability or unwillingness to comply with the medication regimen and/or documentation requirements
- Participant decides to withdraw from the protocol therapy
- General or specific changes in the participant's condition render the participant unacceptable for further treatment in the judgment of the treating investigator

Participants will be removed from the protocol therapy when any of these criteria apply. The reason for removal from protocol therapy, and the date the participant was removed, must be documented in the case report form (CRF). Alternative care options will be discussed with the participant.

In the event of unusual or life-threatening complications, treating investigators must immediately notify the Overall PI, [name], MD.

Confirmation of Progressive Disease

Pembrolizumab, like other immunotherapeutic agents, may produce antitumor effects by potentiating endogenous cancer-specific immune responses. The response patterns seen with such an approach may extend beyond the typical time course of image responses seen with cytotoxic agents, and can manifest as a clinical response after an initial increase in tumor burden or even the appearance of new lesions.

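### Section 5.5 takes participants off both drugs for several toxicities that the eribulin tables in Section 6.1 manage by holding and then resuming or reducing eribulin

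*Combined protocol and SAP*

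**What the plan says.** Section 5.5 lists unacceptable adverse events and other reasons for ending treatment, and then states: "Participants will be removed from the protocol therapy when any of these criteria apply". The list includes "Any grade 4 events except as noted above" and "Any other grade 3 non-skin, drug-related AE lasting >7 days including fatigue". For drug-related autoimmune or inflammatory events of Grade 3 or 4 it names, among others, "diarrhea, colitis, neurologic adverse events, hypersensitivity reaction, or infusion reaction of any duration requires discontinuation except as noted below". Two laboratory exceptions are written out. One spares Grade 3 or 4 laboratory or electrolyte abnormalities that are unrelated to organ pathology and need no treatment beyond electrolytes. The other concerns Grade 3 amylase or lipase. Section 5.5 also says: "Participants requiring > two dose delays for the same type of event should be removed from protocol". It does not mention the eribulin tables.

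Section 6.1 sends eribulin toxicities to Tables 3.1 to 3.5, which mostly hold eribulin and then resume it at the same dose or one level lower. For a first Grade 3 diarrhea that recovers within a week, eribulin "may be resumed at the same dose if deemed appropriate by the investigator, otherwise, reduce by 1 dose level". For Grade 4 anemia, eribulin is held and then reduced, and "PRBC transfusions are permitted to treat anemia on protocol".

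Other places separate the two drugs. Section 5.3.3 says: "If eribulin is stopped for toxicity, participants are permitted to continue protocol therapy with pembrolizumab alone". Section 6 holds only the causal drug, and Section 6.1 allows pembrolizumab when eribulin is delayed or stopped. In Section 6.2, a bullet after Table 4.2 sends expected eribulin-related hematologic events to the eribulin tables without delaying pembrolizumab. The text after Table 4.9 has its own rule for more than two dose delays: pembrolizumab stops, and delays for evaluation are excepted.

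**The concern.** Both sets of instructions are written as rules, and nothing in Section 5.5 says which prevails. A site could answer the same expected eribulin toxicity by continuing the combination with eribulin at a stated level, or by ending both drugs. At stake are consistent safety management, exposure to the combination before the 12-week endpoint, and the reading of tolerability, which is a secondary objective (Section 1.3.2). If sites apply different rules, the numbers of reductions and discontinuations will partly reflect which section was followed.

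**Working it through.** The plan gives no figure on this point, so the check sets the texts side by side and ends with one count.

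**1. What removal covers.** Section 5.3.3 treats pembrolizumab alone as a continuation of protocol therapy. Removal from protocol therapy under Section 5.5 therefore means both drugs.

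**2. Event by event.**

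| Event | Section 6.1 | Section 5.5 | Result |
|---|---|---|---|
| Grade 4 diarrhea (Table 3.1) | Hold, then reduce one level | Removal; neither laboratory exception fits | Clear collision |
| Grade 3 diarrhea (Table 3.1) | First occurrence: reduce if recovery takes over a week. Despite maximal support: reduce | Removal if drug-related and Grade 3 for more than 7 days | Collision when it stays Grade 3 beyond 7 days |
| Grade 3 neuropathy (Table 3.2) | Hold, then reduce one level | As above | Collision when it stays Grade 3 beyond 7 days |
| Grade 4 neuropathy (Table 3.2) | Eribulin stopped for good; pembrolizumab alone allowed | Removal from both drugs | Collision over pembrolizumab only |
| ANC below 500 (Table 3.3) | Hold, then same dose or one level lower, with growth factor | Removal unless the laboratory exception applies | Collision if this is Grade 4 and growth factor counts as treatment |
| Grade 4 anemia (Table 3.5) | Hold, then reduce; transfusion permitted | As for ANC | Collision if transfused and transfusion counts as treatment |
| Grade 4 thrombocytopenia (Table 3.4) | Hold, then reduce; no treatment named | May be exempt if no treatment is needed | Conditional |

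Diarrhea or a neurologic event judged autoimmune or inflammatory falls under the any-duration line of Section 5.5, so the 7-day condition would not then matter.

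**3. The Section 6.2 bullet.** It supports using the tables for hematologic events. It sits in the pembrolizumab section, does not amend Section 5.5, and does not cover diarrhea or neuropathy.

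**4. More than two delays.** Section 5.5 removes the participant from protocol; Section 6.2 stops pembrolizumab and excepts delays for evaluation. One path through Table 3.3, neutropenia with fever or infection, shows the effect:
- First hold, no growth factor: resume at 1.4 mg/m².
- Second hold, despite growth factor: 1.1 mg/m².
- Third hold: the table gives 0.7 mg/m², but if each hold is a delay, the third exceeds two and Section 5.5 removes the participant.

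Other paths differ. ANC below 500 for more than 7 days reduces at the first hold, so 0.7 mg/m² can be reached at the second. Recurrent uncomplicated neutropenia may resume at the same dose. A missed Day 8 dose is skipped, so it may not count as a delay.

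**5. Scale of the Grade 4 part.** Section 2.6 gives 18.7% for Grade 4 treatment-related events in the combination trial.
- All arms: 57 × 0.187 = 10.7, about 11.
- Per arm: 19 × 0.187 = 3.6, so 3 to 4.

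This is an upper guide, because not every such event would meet the conflict. The Grade 3 part cannot be sized, because the documents give no durations.

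**The case against.** The strongest reply is that the intent can be inferred. Section 6.1 points to the tables, Section 6 holds only the causal drug, and the Section 6.2 bullet speaks directly to expected eribulin cytopenias. For cytopenias this is real evidence of intent, and the laboratory exception may spare untreated ones. But the bullet says these events do not even delay pembrolizumab, while Section 5.5 can end it, so the texts still need reconciling.

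It can also be said that slow recovery is not the same as prolonged Grade 3. That stands: diarrhea that is Grade 3 for 4 days and Grade 2 until day 10 is reduced under Table 3.1 and is not caught by the 7-day rule. The collision is limited accordingly.

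The layout of Section 5.5 leaves room for argument too, since the line on prolonged Grade 3 events follows a phrase announcing exceptions. Its wording reads as a further criterion; if sites could take it either way, that also needs correcting. The clinical-judgement sentence in Section 6.1 concerns eribulin and does not waive removal under Section 5.5.

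A reader might infer three stronger things that the documents do not support:
- **Most of the reduction ladder is unreachable.** Intolerable Grade 2 neuropathy still leads to a reduction, as do non-inflammatory Grade 3 diarrhea and neuropathy of 7 days or less. Several other rows conflict only under conditions.
- **About 18 of 57 are affected**, from the 32% Grade 4 neutropenia in Section 2.5.2.5 (57 × 0.32 = 18.2). That figure is for eribulin studies in general. In the combination trial, Grade 3 or 4 neutropenia together was 30.8% and all Grade 4 treatment-related events were 18.7%. The list in Section 7.1.1.2 gives 32% for Grades 3 and 4 combined.
- **The 9-of-19 rule is compromised.** Stopping treatment is not itself a failure under Section 13.1, and Section 5.6 asks for scans after treatment stops for reasons other than progression. No effect on the decision rule is shown.

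**Conclusion.** The contradiction is real but narrower than a first reading of Section 5.5 against the tables suggests. It is unconditional for Grade 4 diarrhea. It holds for Grade 3 diarrhea and neuropathy that stay Grade 3 beyond 7 days and are drug-related. For ANC below 500 and Grade 4 anemia it rests on two assumptions: that ANC below 500 is Grade 4 (the threshold is not printed in the documents), and that growth factor or transfusion counts as treatment under the laboratory exception. Without the second assumption, the firm conflicts shrink to diarrhea and prolonged Grade 3 neuropathy. Grade 4 neuropathy conflicts only over pembrolizumab, and untreated thrombocytopenia may be exempt. The two rules on repeated delays differ and can cut off a later reduction on some paths.

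The Grade 4 count above assumes that the breast cancer rate carries over to sarcoma. The 31.8% who needed an eribulin reduction in that trial cannot refine it, because it is not split by grade or duration. The documents do not show which passage should prevail.

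**What to change.** Reconcile Section 5.5 with Section 5.3.3, Section 6, Tables 3.1 to 3.5, the Section 6.2 bullet on expected hematologic events, and the repeated-delay rule at the end of Section 6.2. For each of the three criteria (Grade 4 events, Grade 3 events beyond 7 days, more than two delays), state:
- whether it applies to events managed by the eribulin tables;
- whether it stops one drug or both;
- for laboratory events, whether growth factor or transfusion counts as treatment under the exception;
- for delays, which holds count, including skipped Day 8 doses and delays for evaluation.

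Then edit the text so that one action remains per event. The sponsor and investigator choose which rule stands. The cost is protocol wording: scope lines in Section 5.5 and matching notes in Section 6, with no added participants, visits or procedures.
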